3.6 CO-ENROLMENT

Participants cannot take part in any other clinical trial of an Investigation Medicinal Product or device whilst taking part in TEMPESTAS until their treatment and follow-up has completed.

Participation in the interventional phase of a non-CTIMP trial while taking part in TEMPESTAS is permissible in accordance with the Sponsor's co-enrolment policy ACCORD POL008.

Contact the trial office if a potential participant is already enrolled in another interventional non-CTIMP.

Co-enrolment with a non-interventional study (sample and/or questionnaire only) is allowed without formal documentation from the Sponsor.

PARTICIPANT SELECTION AND ENROLMENT

3.7 IDENTIFYING PARTICIPANTS

Research staff who may identify potential participants for TEMPESTAS should be part of the clinical team responsible for the patient's care. We have a large COPD and bronchiectasis service in NHS Lothian with over 2,500 patients seen annually. The investigators have a strong record of accomplishment in translational research. Collaborators will be approached from other NHS sites on the basis that they have an equally good repertoire of conducting translational studies with similar set ups.

Research staff who are also part of patient's clinical care team are based at these NHS hospital sites where local resources would facilitate patient identification and eligibility assessment.

Potentially eligible patients would be identified from the NHS clinics or the NHS clinical databases.

3.8 CONSENTING PARTICIPANTS

Patients who consent to be screened will be recorded on the Consent and Subject Status log. The Principal Investigator, Sub Investigator or experienced research nurse will take face-to-face written consent at the screening visit.

Written informed consent must be conducted and obtained before any screening and study procedures are conducted. Patients must receive adequate oral and written information. Sufficient time will be given for the patient to read the Patient Information Sheet (PIS) and

Informed Consent Form (ICF) ask for more information if necessary and clarify any points they don't understand. The patient will be told that they may withdraw their consent to participate at any time without loss of benefits to which they otherwise would be entitled. The process of obtaining informed consent should be documented in the patients' medical record.

As part of the consent discussion, potential participants will be informed that signing the informed consent form does not guarantee their enrolment into the trial. The Screening phase will determine their eligibility.

The participant should receive a copy of their PIS and ICF and a copy should be filed in the patient's medical records. The original PIS and ICF should be filed in the investigator site file (ISF) along with the version of the PIL used.

3.9 SCREENING FOR ELIGIBILITY & WASHOUT

Participant eligibility will be verified by a clinical trial physician after written informed consent has been obtained. Confirmation of eligibility will be recorded within the participants' medical records. The research team will maintain a pre-screening log. Data from this log will be uploaded onto the database.

3.9.1 Screening Logs

The local research team will maintain a pre-screening log.

3.9.2 Screening

All potentially eligible patients will undergo screening to determine whether they are eligible in accordance with the criteria described in Section 4 (exclusion/inclusion).

The screening process begins when the first contact is made by the study team to the patient or the patient contacts the study team using a register of patients who have previously agreed to be contacted for future research. For patients not in the register but deemed appropriate for the study, would be contacted by the PI or the CI (as part of their clinical ongoing care provider responsibility) to obtain a verbal consent prior to intimation by the research team. This contact may be via telephone or face-to face. If the first contact is made via telephone, a copy of the PIS and ICF will be posted to the *patient* and a follow-up call made at least 7 days after where possible to establish whether the patient would like to be screened for participating. If so, a face-to-face screening visit will be arranged. Any further queries would be answered on the day of the face-to-face screening visit.

3.9.3 Washout

Patients must satisfy the study inclusion and exclusion criteria, as possible at this stage during the screening visit to be eligible to receive the washout medication. Eligible patients will be asked to stop their regular inhaler therapy and will receive Anoro Ellipta 55/22 mcg one puff once a day (Long-acting beta agonist/long acting antimuscarinic) for 4 weeks.

Only participants who are eligible for and agree to the 4-week washout will be entered into the eCRF and allocated a trial number.

Patients who do not adhere to the washout treatment regime or do not tolerate the washout medication will be ineligible to be randomised and their participation in the study discontinued.

3.10 INELIGIBLE AND NON-RECRUITED PARTICIPANTS

Patients who are ineligible or not recruited will not be included in TEMPESTAS however they will remain within the clinical service as a part of their standard care of treatment. Their reason(s) for ineligibility will be explained to participants and any questions they have will be answered recorded. They will be thanked for their participation in screening and any relevant clinical information from this visit will be added to their hospital notes and communicated to their GP and consultant where the patient consents for this to happen.

For participants who fail screening this may be repeated and all data will be re-collected.

3.11 RANDOMISATION

3.11.1 Randomisation Procedures

Following successful completion of the 4-week washout phase, verbal reaffirmation will be sought from the patient and recorded in the medical records to collect the baseline data necessary to complete the randomisation and the exclusion criterion would be rechecked.

If still eligible, the participant would be randomised to one of the two arms of the study triple (inhaled corticosteroids/Long-acting beta agonist/long acting antimuscarinic arm) or dual bronchodilator (Long-acting beta agonist/long acting antimuscarinic arm) therapy. Allocation will be made in a 1:1 ratio of study triple: dual bronchodilator using a minimisation algorithm stratified on the following variables: prior ICS (yes/no) and prior long-term macrolides (yes, no). In order to maintain a random allocation, participants will be allocated to the group which minimises the imbalance with a pre-defined probability.

The Investigator will enter the participants data via a 24-hour secure centrally controlled web based GCP compliant central randomisation system, run by the UKCRC registered Edinburgh Clinical Trials Unit (ECTU) using a validated randomisation program and will securely backup both the randomisation seed and the randomisation allocation.

The randomisation system will provide details of the treatment allocation and a confirmatory email will be sent to the PI, RN and local Clinical Trials Pharmacy. The Trial Manager and CI will receive confirmatory treatment allocation emails for all participants at all sites.

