3.11.2 Treatment Allocation

Patients would be randomised to one of the two arms of the study triple (inhaled corticosteroids/Long-acting beta agonist/long acting antimuscarinic arm) or dual bronchodilator (Long-acting beta agonist/long acting antimuscarinic arm) therapy, which is standard treatment for this group of patients.

As the study is not blinded, patients will be aware as to which treatment group they have been allocated.

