6.9 TRIAL DATABASE

A secure trial database will be provided using REDCap and maintained by the Edinburgh clinical Trials Unit. A bespoke randomisation system will be built to manage the randomisation and allocation of IMP. Medication will be automatically assigned once randomised through the randomisation system. This will be linked to REDCap via the REDCap Application Programming Interface (API). Access to the database is role based and site users are restricted to access their own site data only. Trained and delegated members of the study team will be given password-protected logins to the database to complete data entry. All users will require training before access is granted.

The TM and ECTU will provide support for users during working hours. The database will have a secure audit trail and back-up procedures to minimise potential data loss.

Local research staff delegated to do so on the delegation log will enter all trial data into the trial database using eCRF's. Data entry errors will be minimised by using range, completeness and consistency validation checks. REDCap provides the facility for sites to download and print PDFs of the participant's entered data.

The unblinded trial statistician will be given 'read only' access to the database.

Data will be stored on secure servers hosted by the University of Edinburgh that require user authentication, archived after the end of the trial, and made available in de-identified format to satisfy data sharing requirements at the end of the trial.

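### Emailing the CI every allocation at every site is an avoidable weakness in allocation concealment, of modest and uncertain size, in this open-label minimised trial

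*Protocol*

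**What the plan says.** Protocol 3.11.1 describes 1:1 minimisation through a central web system on two yes/no factors: prior ICS and prior long-term macrolides. Site is not a factor. There is a random element: "participants will be allocated to the group which minimises the imbalance with a pre-defined probability". The SAP Introduction also mentions a random component. Neither document gives its size.

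The allocation email goes to the PI, research nurse and pharmacy of the participant's site. In addition, "The Trial Manager and CI will receive confirmatory treatment allocation emails for all participants at all sites". What the emails contain beyond the allocation is not described.

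On the CI's part in recruitment, 3.9.2 says that suitable patients who are not on the research register "would be contacted by the PI or the CI", as their care provider, before the research team approaches them. Section 3.11.2 confirms the open design: "As the study is not blinded, patients will be aware as to which treatment group they have been allocated". Section 6.9 limits database access: "site users are restricted to access their own site data only". It does not say what the CI's own role-based access covers.

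**The concern.** Under minimisation, the favoured arm for the next participant follows from the allocations already made. Someone who sees only one site's allocations knows little about the trial-wide totals. Someone who sees every allocation as it happens can track them. The emails put the CI, who may also approach patients, in that second position, and neither document gives a reason for routine real-time notice of other sites' allocations.

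If the likely next arm can be guessed, a borderline eligibility decision can be influenced by it, knowingly or not. The arms may then differ in prognosis. Blinding the microbiology laboratory (Protocol 5.6, SAP 4.9) protects how the primary outcome is measured, not who enters each arm. The primary analysis is an unadjusted t-test on change (SAP 4.4), so it would not correct for such a difference.

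**Working it through.** **The plan's own figure.** Protocol 8.1 gives a difference of 0.76 log, SD 0.98, two-sided 5% and 90% power. The normal approximation is n = 2 × (1.960 + 1.282)² × (0.98/0.76)² = 34.9, so 35 per arm. The t-test solution is 35.93, so 36 per arm (power 90.1%). With 10% dropout, 36/0.9 = 40 per arm, 80 in total. The stated size reproduces and this point does not affect it. The 0.76 and 0.98 serve below only as a scale.

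**Predicting the next arm.** The documents give no figure, so the scheme was simulated.

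- From the documents: 80 participants, 1:1, two binary factors, no site factor, 3 to 6 sites.
- Assumed: probability p of allocating to the minimising arm, 0.6 to 0.9; equal factor weights; ties broken 50:50; factor prevalences 50%/50%, 80%/20% and 90%/10%; own-site share 1/6 to 1/2.
- Method: 600 simulated trials per setting. The guesser names the arm that would reduce the imbalance visible to them and tosses a coin when it is tied.

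Percentage of correct guesses (chance is 50%):

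| p | All-site arm totals only | All-site arms and factor values | Own-site data only |
|---|---|---|---|
| 0.6 | 55-56 | 59 | 51-53 |
| 0.7 | 60-61 | 67 | 52-54 |
| 0.8 | 64-65 | 74 | 52-55 |
| 0.9 | 68 | 80 | 52-55 |

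Factor prevalence moves the all-site figures by about one point. Own-site data stay within 51-56% even at p = 1.0. The all-site information therefore creates most of the predictability.

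**When prediction could be used.** The contact in 3.9.2 comes before the four-week washout. Assuming accrual over 30 - 12 = 18 months, 80/18 = 4.4 participants a month, so about four allocations are still to come at that point. With the last four allocations unknown and p from 0.6 to 0.9, correct guesses fall to 52-54% (arm totals) or 55-58% (with factor values). The figures in the table apply only to the next allocation, that is, at the exclusion recheck just before randomisation.

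**Illustrative bias.** Suppose that a share s of patients is steered by ±η SD according to a guess that is right with probability g. The expected difference between arms is then 2 × η × (2g - 1) × s × SD. Take η = 0.25 (assumed), SD = 0.98 and g = 0.64 (arm totals, p = 0.8).

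- s = 0.25: 2 × 0.25 × 0.28 × 0.25 × 0.98 = 0.034 log; 0.034/0.76 = 4.5%.
- s = 0.50: 2 × 0.25 × 0.28 × 0.50 × 0.98 = 0.069 log; 0.069/0.76 = 9%.
- Own-site data for comparison, g = 0.54: 2 × 0.25 × 0.08 × s × 0.98 = 0.010 to 0.020 log, or 1-3% of the target.

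**The case against.** A reader might infer that the CI can predict assignments well above chance and so control who is randomised and when. The documents do not support this, for several reasons.

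- **Prediction.** Its strength rests on an unstated probability and unstated email content. At p = 0.6 with arm totals only, it is about 56%. Nothing shows that the CI receives other sites' factor values.
- **The decision-maker.** Consent is taken by the PI, a sub-investigator or a nurse (3.8). A trial physician verifies eligibility (3.9), and the Investigator enters the randomisation data (3.11.1). No section says that the CI makes the post-washout decision.
- **Timing.** Table 1 fixes Visit 2 at four weeks ±2 days, which at 4.4 participants a month spans less than one expected allocation. A failed screen may be repeated, but all data are collected again (3.10) and randomisation still follows a four-week washout, so prediction decays again.
- **Discretion.** No ECG is scheduled at Visit 2, and washout adherence is a 50% threshold read from the dose indicator.
- **Purpose.** The CI has trial-wide duties, such as decisions on stopping IMP (3.2) and upgrading adverse events (9.4), so some access to allocations is legitimate.

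Most of this stands, and it limits the size of the problem. It does not remove it. Some exclusions still turn on judgement at the recheck (3.5 items 9, 13 and part of 19), and 4.4 allows exceptional circumstances to excuse low washout adherence. The CI's duties concern particular participants and can be met by access on request.

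**Conclusion.** The all-site emails are an avoidable allocation-concealment weakness. They raise correct guessing of the next arm from about 51-56% (own-site data) to about 56-68% on arm totals, or 59-80% if factor values are known, for an assumed p of 0.6 to 0.9. The exposure is mainly at the post-washout recheck and depends on the CI taking part in it, which is not documented.

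Any bias is likely small, about 0.03-0.07 log at p = 0.8 on arm totals. That figure rests on an assumed steering size and share that nothing in the documents supports or rules out. A larger figure is tempting: with g = 0.74 the same formula gives 2 × 0.25 × 0.48 × s × 0.98 = 0.06 to 0.12 log, or 8-15% of the target. It requires factor values that the emails are not said to carry, so it should not be used as the estimate.

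This is a minor point, worth acting on because the remedy costs almost nothing.

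**What to change.** While recruitment is open, amend 3.11.1 as follows:

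- All-site allocation emails go only to the Trial Manager, provided that this role takes no part in recruitment.
- The CI receives allocations only for participants at the CI's own site, or for a named participant when a safety or treatment decision needs it.
- The emails omit the minimisation factor values.
- Cumulative allocations and the minimisation probability are withheld from anyone who recruits until recruitment closes.

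Site should stay out of the minimisation, because adding it would make own-site prediction easier.

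The cost is a short protocol change and a new recipient list in the existing randomisation system, with no extra patients or procedures. The downside is that the CI loses the routine real-time view of other sites' allocations.

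SAP version 2.1 is dated June 2025 and describes some scoring as already done, so recruitment may have closed. In that case, report the arrangement as a limitation and compare baseline balance between arms at the CI's site with that at the other sites. The SAP 4.3 tables are split by arm but not by site, so this would be one additional table.

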3.11.2 Treatment Allocation

Patients would be randomised to one of the two arms of the study triple (inhaled corticosteroids/Long-acting beta agonist/long acting antimuscarinic arm) or dual bronchodilator (Long-acting beta agonist/long acting antimuscarinic arm) therapy, which is standard treatment for this group of patients.

As the study is not blinded, patients will be aware as to which treatment group they have been allocated.

3.12 WITHDRAWAL OF STUDY PARTICIPANTS

3.12.1 Study Withdrawal

Participants are free to withdraw from the study at any point or a participant can be withdrawn by the Investigator. If withdrawal occurs, the primary reason for withdrawal will be documented

in the participant's eCRF, if specified by the patient. The participant will have the option of withdrawal from:

- (i) study medication with continued study procedures and collection of clinical and safety data. The final Assessment Visit should be brought forward and they will receive the final follow-up contact.
- (ii) all aspects of the trial but continued use of data collected up to that point. To safeguard rights, the minimum personally-identifiable information possible will be collected. Any patient who withdraws from all aspects of the study will be invited to return to the clinic to have a Final Assessment Visit.

Data will be kept on the CRF/database.

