3.3 NUMBER OF PARTICIPANTS

We aim to recruit 80 patients with moderate-severe COPD with coexistent diagnoses of radiological proven bronchiectasis. Patients will be followed up for 12 months after randomisation.

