3.12.4 Follow-up contact

A safety follow-up contact will be made 7 days (-1/+4) following the completion of the randomised treatment period at 12 months or following the Final Assessment Visit (whichever comes first).

The follow-up contact can be made by phone call or by site visit. The following procedures will be performed:

- Adverse event assessment
- Concurrent medication assessment
- COPD exacerbation assessment

Subjects who have successfully completed all on-treatment randomised visits will be discharged from the study upon completion of the safety follow-up contact.

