4.5 OVERDOSE

Vilanterol: An overdose would likely lead to effects that are typical for $\beta 2$ adrenoceptor agonists: tremor, headache, and palpitations. Supportive and symptomatic treatment may be indicated.

Fluticasone: Acute inhalation of doses in excess of those recommended may lead to temporary suppression of adrenal function. This does not need emergency action as adrenal function is recovered in a few days.

Umeclidinium: Acute over dosage is not expected to be a clinical problem. Warning would however be issued around usual side effects like visual disturbances, dry mouth, constipation, micturition difficulties and tachycardia. Treatment is usually observation and symptomatic management.

Other side effects to watch out for: of study drugs are likely to be minor and expected. Candidiasis is the main side effect and withdrawal from study treatment will occur if it is marked as persistent and does not respond to symptomatic treatment. Patients should receive treatment with Nystatin 100,000 units four times daily for up to 7 days if candidiasis requires symptomatic treatment. Requirement for another or additional treatment should lead to study withdrawal as alternative treatments may impact the primary outcome.

Paroxysmal bronchospasm is a rare side effect (≥1/10 000 to <1/1000) any patients experiencing this would be withdrawn from treatment, the patient will be assessed, and an alternative therapy instituted, if necessary.

If patients withdraw from the study at some during the trial and do not wish to return for study visits, contact with them will be maintained by the PI, trial manager, research nurse or research assistant to ensure resolution of adverse event(s) and their GP notified. If withdrawal is due to an AE, it will be logged as such on the Adverse Event Log.

The following table summarises the strategy to mitigate some possible side effects from the proposed IMPs.

Potential Risk of Clinical Significance		Mitigation Strategy

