5.3 STUDY ASSESSMENTS

Investigations (A	All Patients)	Screening and Consenting Visit	Medication Washout Period 4 weeks	Baseline/Randomisation	Telephone Follow-up contact	Month 6 +/- 2 Weeks	Month 12 or Final Assessment +/- 3 Weeks			Exacerbation Visit (Face to face or telephone visits)
Visit Number		Visit 1		Visit 2	Visit 3	Visit 4	Visit 5	Visit 6 *	Visit 7	As necessary
Time relative to	randomisation	- 4w	-4w	0	1m + 2d	6m	12m	1 to 12m	12m + 7d	1 to 12
Time window fo	or evaluation	N/A	N/A	4 weeks ±2 days from screening		+ 2 weeks from randomisation	+ 3 weeks	+2d	+3d	-
Written Informe		✓								
LMP, Pregnancy review (where a	Test & Contraception applicable)	✓		√		✓	✓		✓	
Physical Examin and weight)	ation (including height	✓								✓
Current COPD M	ledications?	✓		✓	✓	✓	✓	✓	✓	✓
Concomitant Me	edications	✓								
Past Medical His	story?	✓								
Demographics		✓								
Stratification				✓						
Lifestyle		✓								
Eligibility review		✓		✓						
Reaffirm Conser				✓		✓	✓		✓	✓
Medication Was	hout & Accountability			✓						
Randomisation				✓						
Spontaneous Sputum	Sputum Colour			✓		✓	✓		✓	
Sputum	Qualitative and Quantitative Microbiology 16S RNA Pyrosequencing			√		√	✓			
Sputum inflammatory assays	Myeloperoxidase (MPO) Free elastase activity			✓		· ·	✓		- v	

Routine Bloods	FBC including								
tests	eosinophil count,				✓	√		1	
	CRP, ICAM-1		ľ		•	•		•	
	U&E's, LFT's								
	Fibrinogen								
Spirometry	FEV1 + FVC;								
	FEV1/FVC; mid	✓	✓		✓	✓		✓	
	expiratory flows								
	(FEF25-75)								
Questionnaires	COPD Assessment								
	Tool		 		✓	✓		✓	✓
	St George's		·		·				
	Respiratory SGRQ-C								
	eathlessness score	✓	✓		✓	✓		✓	
12 Lead ECG		✓			✓	✓		✓	
Vital signs (Pulse, respiratory rate,									
blood pressure, oxygen saturations on		✓	✓		✓	✓		✓	✓
room air and body temperature)									
Exacerbations (Number of and time to			✓	✓	✓	,	✓	√	
1st moderate/sev	vere exacerbation)		V		v	✓		•	
Collection of all AE and SAE data (as in			,	✓	,	,	✓	,	,
section 11)	section 11)		✓		✓	✓		✓	✓
Dispense randomised study			✓		✓				
Medication?									
Study Medication	Study Medication Adherence (&			✓	✓	✓		✓	✓
Accountability check if face to face)									
	,					✓			
						,			
						✓			
								✓	✓

Table 1 of assessments

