6.4 Visit 5 – 12 months/Final Assessment

A final Assessment Visit will be completed for all participants at completion of the study or earlier if required.

The following assessments are expected to be conducted in clinic and must be recorded in the CRF:

- Adverse Events
- Any exacerbations of COPD
- Any changes in concomitant medications
- Pregnancy and contraceptive review (if there is concern of pregnancy, another pregnancy test will be administered)
- Vital signs
- Blood analysis (Biochemistry)
- Sputum collection
- ECG
- ICAM-1 collection
- Adherence to study treatment
- Spirometry
- SGRQ-C assessments
- COPD Assessment Tool (CAT)
- Modified MRC breathless score

- Return of unused study medication and accountability
- Study medication adherence and accountability

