8. STATISTICS AND DATA ANALYSIS

8.1 SAMPLE SIZE CALCULATION

With a sample size of 36 per group we would be able to detect a difference of 0.76 log unit in the change in bacterial load between treatment arms assuming a common standard deviation of 0.98 log units based on a two-sided, two-sample test with 5% level of significance and 90% power¹⁹. A 10% drop out rate increases this to 80 patients (40 per group).

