3.1 Analysis populations

Participants will be included in the analysis in the groups to which they were originally assigned irrespective of treatment actually received with the exception of adverse event data which will also be presented by treatment received.

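### Protocol 3.12.1(i) keeps drug-only stoppers in study procedures but uses up their month-12 visit early, so the primary analysis has no scheduled 12-month sputum culture for them

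*Protocol*

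**What the plan says.** Protocol 3.12.1 offers two kinds of withdrawal. Option (i) is from study medication only, with procedures and clinical and safety data collection continuing. The next sentence reads: "The final Assessment Visit should be brought forward and they will receive the final follow-up contact". Option (ii) is from all aspects of the trial, with an invitation to a Final Assessment Visit.

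The Final Assessment is not a separate visit. Table 1 in Protocol 5.3 has a single Visit 5 column headed "Month 12 or Final Assessment +/- 3 Weeks", and Protocol 6.4 says: "A final Assessment Visit will be completed for all participants at completion of the study or earlier if required". Protocol 3.12.4 times the closing safety contact at 7 days "following the completion of the randomised treatment period at 12 months or following the Final Assessment Visit (whichever comes first". That contact covers adverse events, medication and exacerbations, not sputum.

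Protocol 3.3 states a fixed follow-up: "Patients will be followed up for 12 months after randomisation". SAP 3.1 says: "Participants will be included in the analysis in the groups to which they were originally assigned irrespective of treatment actually received". SAP 4.4 defines the primary outcome as log CFU per mL at 12 months minus log CFU per mL at baseline, compared by a two-sample t-test. SAP 3.4 plans no imputation and mentions only a possible, unspecified sensitivity analysis.

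Drug-only stopping is foreseen. Option (i) exists for it, SAP 4.5.10 counts dropout from study drug alone because of worsening COPD, and Protocol 4.5 withdraws from treatment any participant with paroxysmal bronchospasm.

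**The concern.** The two sentences of option (i) pull in opposite directions. The first keeps the participant in the study's procedures. The second spends the only visit that could supply the 12-month culture and moves to the closing contact. A site that follows the second sentence obtains a sample at drug stop and nothing at month 12.

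Two things can then happen at analysis. The participant has no 12-month value and drops out of the t-test, or the early sample, filed as Visit 5, is taken as the 12-month value. SAP 4.4 does not say how an early Visit 5 sample is handled.

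The trial is open label, only one arm contains a corticosteroid, and participants with prior ICS use can be allocated to the arm without it. Stopping could therefore differ by arm, and stopping for worsening COPD could be related to bacterial load. If both hold, a comparison without the stoppers is biased for the as-randomised difference. A month-12 sample that was never taken cannot be recovered at the analysis stage.

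**Working it through.** **Is a 12-month culture scheduled elsewhere?** As far as Table 1 can be read, the quantitative microbiology row has three ticks, which fit baseline, month 6 and Visit 5. Protocol 6.2 to 6.4 list sputum collection at those same three visits. No section schedules a second Visit 5. After an early Final Assessment, no 12-month culture remains on the schedule.

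**The plan's own figure.** Protocol 8.1 gives a difference of 0.76 log, SD 0.98, two-sided 5%, 90% power and 36 per group. The noncentrality is 0.76 / (0.98 × √(2/36)) = 3.29, and the noncentral t gives 90.1% power. With 35 per group it is 89.2%, so 36 is reproduced. 36 / 0.9 = 40 per group, 80 in all.

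**Assumptions.** The documents give no rate of drug-only stopping. The 10% allowance (8 of 80) must also cover death, loss to follow-up and full withdrawal. I assume half of it, 4 participants, are drug-only stoppers, and that their 12-month change differs from completers' by 0.5 to 1 log, in the same direction in both arms.

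**Bias if stoppers are missing.** An arm's as-randomised mean differs from its completers' mean by (stoppers / 40) × gap. The error in the arm difference is therefore (stoppers in A / 40 − stoppers in B / 40) × gap. The false-positive rate is the two-sided rejection probability of the t-test when there is no true effect and the mean difference equals that bias.

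| Split of 4 | Gap (log) | Bias (log) | Share of 0.76 | n per arm | False-positive rate |
|---|---|---|---|---|---|
| 2 vs 2 | any | 0 | 0% | 38/38 | 5.0% |
| 3 vs 1 | 0.5 | 0.05 × 0.5 = 0.025 | 3% | 37/39 | 5.1% |
| 3 vs 1 | 1 | 0.05 × 1 = 0.05 | 7% | 37/39 | 5.6% |
| 4 vs 0 | 0.5 | 0.10 × 0.5 = 0.05 | 7% | 36/40 | 5.6% |
| 4 vs 0 | 1 | 0.10 × 1 = 0.10 | 13% | 36/40 | 7.2% |

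Removing the other 4 budgeted losses, 2 per arm, barely changes this: 5.1% and 5.5% for 3 vs 1 (35/37), 5.5% and 7.1% for 4 vs 0 (34/38).

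A 10% false-positive rate needs a bias of about 0.15 log. Since 0.15 = 6/40 × 1 = 12/40 × 0.5, that means 6 more stoppers in one arm than the other at a 1-log gap, or 12 more at 0.5 log.

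**Power.** With the 4 stoppers missing and 4 other losses, 36/36 gives 90.1%. With the stoppers followed (2 per arm, 38/38), power depends on how much of the effect they keep:
- none kept: 0.76 × 36/38 = 0.72, power 88.5%
- half kept: 0.74, power 90.1%
- all kept: 0.76, power 91.6%

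The 88.5–91.6% range also applies if their early samples are counted as 12-month values. If 10% of all 80 stopped, all were followed (40/40) and none kept the effect, the difference is 0.76 × 0.9 = 0.684 and power is 86.9%.

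If drug-only stoppers instead came on top of the 10% allowance and were missing, 5% more leaves 34 per arm (88.3%), 10% leaves 32 (86.3%) and 20% leaves 28 (81.3%).

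**The case against.** The strongest case against is that the loss is inferred. Option (i) expressly keeps procedures going, and nothing forbids a month-12 sample. That stands as far as it goes: the protocol does not prohibit the sample. But no visit schedules one, and the instruction leads straight to the closing contact.

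A reader might infer that SAP 3.1 promises every randomised participant a 12-month value. It does not. It fixes the group in which a participant is analysed. The plan can also be read as treating drug-only stoppers as dropouts: SAP 4.5.10 groups them with other dropouts, and Protocol 8.1 allows for loss: "A 10% drop out rate increases this to 80 patients (40 per group". The difficulty is that this reading sits badly with Protocol 3.3 and with the first sentence of option (i).

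A reader might also take candidiasis as the main route to drug-only stopping, because Protocol 4.5 says "withdrawal from study treatment will occur if it is marked as persistent and does not respond to symptomatic treatment". The same paragraph sends a participant who needs other or additional treatment to withdrawal from the study, so it is a weak example. Paroxysmal bronchospasm, SAP 4.5.10 and option (i) itself carry the point.

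An end-of-treatment sample is a defensible choice in a proof-of-concept trial. Later sputum may reflect other inhalers, and Protocol 4.5 and 4.7.3 show concern about treatments that alter the bacteriology. This stands as a cost of following stoppers, but the protocol does not state that choice.

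A stated 12-month window in the SAP would add little, since SAP 4.4 already specifies 12 months and Table 1 gives the window. Used alone, it would also exclude the only late sample of anyone closed out early. Finally, the SAP is dated June 2025 and describes some work as done, so an amendment may come late. The documents do not state how many participants remain in follow-up.

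**Conclusion.** The point holds as an internal contradiction in Protocol 3.12.1(i) that leaves drug-only stoppers without a scheduled 12-month culture and leaves their place in the primary t-test unsettled. Priority is low to moderate.

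The size rests wholly on assumed numbers of stoppers, splits between arms and gaps from completers. With 4 stoppers the bias runs from zero (balanced) to 0.10 log (all in one arm, 1-log gap), with a false-positive rate of at most about 7%. The upper end uses a gap larger than the 0.76 target effect. Reaching 10% would need an excess of 6 stoppers in one arm, which 4 stoppers cannot produce.

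A reader might infer that the trial is underpowered or its primary result invalid. The documents support neither. The sample size reproduces, and power stays near 90% if drug-only stoppers fall within the 10% allowance. What is at stake is which effect is estimated and a possible, probably small, bias.

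**What to change.** **Protocol 3.12.1(i).** For participants who stop study drug only, delete the sentence that brings the Final Assessment forward. Keep their remaining month-6 and month-12 visits with sputum. Record any visit at drug stop as an end-of-treatment visit, not as Visit 5. Keep the early Final Assessment for full withdrawal under (ii).

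**Participants already closed out early.** In the SAP, take only sputum within 12 months ± 3 weeks as the 12-month value in the primary t-test, and show the early Final Assessment samples in a sensitivity analysis. This makes their handling explicit and keeps their data in view, but does not remove missing-data bias. The two-sample t-test stays as planned.

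**Cost.** One protocol amendment, a short SAP addition, and up to two already planned visits per stopper (at most 8 visits for 4 stoppers, 16 for 8). As-randomised power falls slightly if stoppers lose the effect: 88.5% with 4 stoppers and none of it kept. The amendment helps only participants who have not yet been closed out.
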